WARD - Circadian analysis

Clinicaltrials.gov identifier NCT05347784

Statistical analysis plan

Version 1.1

June 9th 2023

Method

Patients

This analysis is a part of the Wireless Assessment of Respiratory and circulatory Distress (WARD) project.

The study is a nested case-control study, using patient vital sign data from 3 previous observational cohort studies of postoperative patients.

Clinicaltrials.gov identifiers:

- NCT03491137 (n=491)
- NCT04473001 (n=70)
- NCT04628858 (n=40)

All patients in the studies above have had the following vital signs recorded:

- Heart rate (HR)
- Respiration frequency (RF)
- Peripheral arterial oxygen saturation (SpO₂)
- Blood pressure (BP).

All values except BP have been recorded continuously with a 1-minute sampling rate. BP was recorded every 30 minutes during the daytime and every 60 minutes during the night.

Manual intermittent vital sign measurements were collected from electronic health records for study NCT03491137, and National Early Warning Score values will be calculated from these.

Outcomes

The primary outcome defining the case population is patients that have any postoperative serious adverse event (SAE) occurring from the start of vital sign monitoring in the ward, and up to 24 hours after vital sign monitoring. The control population will be the patients that have no recorded postoperative SAE up to 30 days after surgery. For patients with several outcomes, only measurements in the 24-hour period

preceding the first SAE were chosen for analysis. We also censored the last hour before an outcome, as this time is expected to represent the delay between clinical suspicion and confirmation by a diagnostic test for the specific SAE. For the population with no 30-day SAE, all recorded 24-hour periods were used to calculate exposure variables.

Outcomes for all studies were assessed using a standardised manual that was constructed before outcome evaluation. The definition of an SAE was taken from good clinical practice guidelines:

“any untoward medical occurrence that at any dose: – results in death,– is life-threatening,– requires inpatient hospitalisation or prolongation of existing hospitalisation, results in persistent or significant disability/incapacity, or is a medically important event or reaction.“.

Circadian definitions

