Six different ‘windows’ of circadian rhythm were defined from the literature: night-time nadir, peak-to-trough, morning activation, daytime acrophase, afternoon local minimum, and evening deactivation.

Exposures

The primary exposure is the lowest vital sign values at night-nadir, as these values are thought to represent a period of least physiologic stress, and unbiased from movement, and other voluntary activity. Secondary exposures are the lowest vital sign values at the other circadian windows. We also include manually measured NEWS values in the secondary analyses.

Analyses

We did not perform a power analysis prior to analyses due to the nested case-control design.

To avoid calculating values for circadian windows with only limited data, we introduced a minimum data condition, requiring 66 % of data for a specific window-vital sign combination.

A p-value of <0.01 was considered significant to account for multiple statistical testing.

Primary analysis

The primary analysis is descriptive

Secondary analyses

Secondary analyses were a calculation of risk ratios (RR).

For this, Youden's optimal cut-off values will be calculated for each window-vital sign combination.

Afterwards, values for each patient are split into above or below Youden's optimal cut-off point, and risk ratios will be calculated from this discrimination.

For NEWS measurements, a cut-off was defined as a total NEWS score ≥ 6 or a single-parameter score of 3.

Sensitivity analysis

We will also include calculations of fitted cosine curves to vital values, from which rhythm-adjusted mean value (MESOR) and amplitude can be calculated.

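### Every vital-sign risk ratio rests on an above/below split at a Youden cut-off; a full-scale model would keep about a third more of the information and remove the over-rejection that the split brings

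*SAP*

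**What the plan says.** Under Secondary analyses, the SAP first derives the cut-offs: "Youden's optimal cut-off values will be calculated for each window-vital sign combination". It then states that "values for each patient are split into above or below Youden's optimal cut-off point, and risk ratios will be calculated from this discrimination". With six circadian windows and four vital signs this makes 6 × 4 = 24 combinations. No external or hold-out data are mentioned for choosing the cut-offs, and no correction for choosing them.

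Under Analyses, the significance rule is: "A p-value of <0.01 was considered significant to account for multiple statistical testing". Neither the sidedness nor the test attached to the risk ratio is named. On size, the same section says: "We did not perform a power analysis prior to analyses due to the nested case-control design".

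The other analyses do not supply an association measure on the measured scale. The primary analysis is descriptive. The sensitivity analysis calculates MESOR and amplitude from cosine fits but sets out no model relating them to case status. NEWS alone has a cut-off fixed in advance.

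**The concern.** The exposures are numeric, yet each is reduced to two groups before any association is estimated. Patients just either side of the cut count as different; patients at the two ends of one side count as the same. No clinical or guideline reason is given for cutting the four vital signs.

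Two things are at stake. The first is lost information: with at most 491 + 70 + 40 = 601 patients, cases limited to events during monitoring or within 24 hours after it, and a strict 0.01 level, a valid test on the split would miss more real associations than one on the full scale. The second is validity: if the cut is chosen and tested in the same patients, the 0.01 level is not kept and the risk ratio is too large. Correcting the second problem alone would leave the first.

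**Working it through.** The SAP states no power, effect size or number of cases, so there is no figure of its own to reproduce.

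**Inputs from the SAP.** Level 0.01 (two-sided assumed, and assumed to apply to the risk ratio). N at most 601; the 66% minimum-data rule will reduce it for each combination.

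**Assumptions.** One value per patient; normal values with equal SD; cases differ from controls by d SD in one direction; cases 10, 20 or 30%; d = 0.2 to 0.6; N = 300, 450 or 601.

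**Step 1: information kept.** For small d, a cut in the middle of a normal variable has efficiency φ(0)²/0.25 = 2/π = 0.637. It keeps about 64% and loses about 36%. In effect, 0.637 × 601 ≈ 383 patients are analysed.

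**Step 2: power with a cut fixed in advance.** For two equal-SD normals the population Youden point is the midpoint, so the shares above it are Φ(d/2) in cases and Φ(−d/2) in controls.

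- Full scale: power = Φ(d·√(n₁n₀/N) − 2.576).
- Cut: power = Φ([p₁ − p₀ − 2.576·SE₀]/SE₁), with SE₀ pooled and SE₁ unpooled.

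Example, N = 601, 20% cases, d = 0.3. Full scale: 0.3 × √(120.2 × 480.8/601) = 2.942, so Φ(0.366) = 64.3%. Cut: p₁ = 0.5596, p₀ = 0.4404, SE₀ = 0.0509, SE₁ = 0.0506, so power is 40.8%. Loss 23.5 points.

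N = 601, full scale vs cut (%), loss in points from unrounded values:

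| d | 10% cases | 20% cases | 30% cases |
|---|---|---|---|
| 0.2 | 13.5 vs 8.0 (5.4) | 26.9 vs 15.5 (11.4) | 37.1 vs 21.6 (15.6) |
| 0.3 | 35.6 vs 20.7 (14.9) | 64.3 vs 40.8 (23.5) | 78.7 vs 54.3 (24.4) |
| 0.4 | 64.3 vs 41.1 (23.2) | 91.1 vs 70.9 (20.2) | 97.2 vs 84.2 (13.0) |
| 0.5 | 86.5 vs 64.3 (22.1) | 99.0 vs 91.0 (8.0) | 99.9 vs 97.2 (2.7) |

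Over all 45 settings (3 values of N, 3 case fractions, 5 values of d) the loss runs from 0.2 to 24.7 points and is at least 10 points in 30. It is small where power is very low or near 100%. Simulated robust-Poisson risk ratios per SD agree with the full-scale column (N = 601, 20% cases: 28.1, 64.4 and 90.3% at d = 0.2, 0.3 and 0.4).

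**Step 3: the split as the SAP describes it.** Simulation with the Youden cut chosen in the same data, N = 601, 20% cases, rejection rate (%):

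| d | Full scale | Youden, critical value 2.58 | Youden, recalibrated to a true 1% (3.56) |
|---|---|---|---|
| 0 | 1.1 | 12.9 | 1 by construction |
| 0.2 | 28.1 | 54.6 | 15.0 |
| 0.3 | 65.4 | 83.7 | 39.8 |
| 0.4 | 90.8 | 96.5 | 70.2 |

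Across the settings run, the false-positive rate is 12 to 14% if the cut may point either way and about 7 to 7.5% if its direction is fixed. At d = 0.3 the median Youden risk ratio is 1.79, against a geometric mean of 1.48 with the cut fixed in advance. With no association at all, the median is 1.40 in one direction or the other.

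Once recalibrated, power falls to about that of the pre-fixed cut: 28.1 − 15.0 = 13.1, 65.4 − 39.8 = 25.6 and 90.8 − 70.2 = 20.6 points below full scale. In the thinnest setting run (N = 300, 10% cases, d = 0.5) the gap is 50.2 − 22.4 = 27.8 points.

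**The case against.** A reader might infer that the plan as written will miss associations at 0.01. The text does not support that. Nothing in the SAP fixes the cut in advance or recalibrates the test, and used as described the split rejects more often than the full-scale test, not less. The power loss applies to a test that holds its level. The immediate defects of the written plan are false positives and inflated risk ratios. This objection stands, but it does not rescue the split, because rejections gained by breaking the level are not power.

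A reader might also infer that most of the measurement is thrown away. A middle cut loses about 36% of the information. Nor does the recording frequency ("All values except BP have been recorded continuously with a 1-minute sampling rate") enlarge this: the exposure is the lowest value in a window, so the minute-level series is already reduced before any cut.

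It would also be wrong to set the spread of above/below risk ratios against the spread of risk ratios per SD. The scales differ: the two halves of a normal variable lie about 1.6 SD apart.

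The sizes depend on assumptions that favour a linear full-scale term. SpO2 is bounded at 100%, window minima need not be normal, and risk may be U-shaped in heart rate, respiration frequency or blood pressure, where a linear term could also miss it. That stands, and it is why the test must allow for curvature. Above/below risk ratios also sit naturally beside the NEWS threshold risk ratio. The SAP does not state that purpose, but it is a fair reason to keep the cut-off table.

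**Conclusion.** The point holds as an avoidable weakness of the secondary analyses; the descriptive primary analysis is untouched. For a test that keeps the 0.01 level, splitting costs about 0 to 25 points of power, and 10 to 25 in most mid-range settings. This rests on normal, equal-SD, monotone effects and on assumed case fractions, effect sizes and evaluable N, none of which the SAP gives. Tested as written, the split has about 7 to 14% false positives in place of 1%, on the reading that cut and test use the same patients without correction. The SAP does not say this outright, but it names no alternative. A full-scale model removes both problems.

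**What to change.** For each window and vital sign, make the p<0.01 inference a full-scale model of case status: modified Poisson regression with robust variance, or logistic regression. Report the RR or OR per SD and per clinical unit with a 99% CI. Where risk may be non-monotone (heart rate, respiration frequency, blood pressure), include a restricted cubic spline with knots fixed in advance and apply the p<0.01 rule to the overall association test. Keep the Youden cut-off and its risk ratio as a descriptive table without p-values, beside the NEWS threshold risk ratio.

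The cost is SAP wording and a few lines of code on data already held. There are four drawbacks:

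- A per-SD effect is less direct to read than above/below.
- It is not directly comparable with the NEWS threshold risk ratio.
- A linear term can lose power if the true relation is a sharp threshold.
- The spline's overall test gives back part of the gain when the relation is in fact linear. With two degrees of freedom (critical χ² 9.21, noncentrality 2.942² = 8.65; N = 601, 20% cases, d = 0.3), power is 53.1%, between 64.3% for the linear term and 40.8% for the cut.

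### Youden cut-offs are chosen and the risk ratios computed in the same patients with no correction, so the risk ratios are inflated and a p<0.01 test of them would run at about 0.04–0.13

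*SAP*

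**What the plan says.** The relevant text is in four places in the SAP.

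- **Cut-off and effect measure (Secondary analyses).** Youden's "optimal cut-off values will be calculated for each window-vital sign combination". Then "values for each patient are split into above or below" the "optimal cut-off point, and risk ratios will be calculated from this discrimination". No validation set, resampling correction or search-adjusted test is mentioned. The RR is the only effect measure named, with no test and no expected direction of risk.
- **Error control (Analyses).** "A p-value of <0.01 was considered significant to account for multiple statistical testing". This is the only error-rate figure in the SAP.
- **Number of combinations (Patients; Circadian definitions).** There are four vital signs (heart rate, respiration frequency, SpO₂, blood pressure) and six windows: "night-time nadir, peak-to-trough, morning activation, daytime acrophase, afternoon local minimum, and evening deactivation".
- **NEWS (Secondary analyses; Patients).** NEWS alone has a threshold set in advance: "For NEWS measurements, a cut-off was defined as a total NEWS score" of at least 6, or 3 on one parameter. It is available for one cohort only, "collected from electronic health records for study NCT03491137, and National Early Warning Score values will be calculated from these".

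**The concern.** Youden's rule searches every possible threshold for the largest gap between sensitivity and false-positive rate. An RR computed at that threshold in the same patients measures real separation plus whatever chance separation the search found. It therefore tends to exceed 1 in the apparent direction even when the vital sign carries no information. The SAP does not say in so many words that the same patients are used, but it describes one dataset and splits every patient in it, so that is the plain reading.

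The p<0.01 rule does not repair this. Its stated reason is the number of tests, and it makes no allowance for the search within each one.

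A reader could not tell such an RR from a modest real effect. If the NEWS RR, which has a fixed threshold, is read beside the window RRs, the reading favours the windows.

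**Working it through.** **Inputs from the SAP.** Cohorts 491 + 70 + 40 = 601 patients before exclusions; 4 vital signs × 6 windows = 24 combinations at least; threshold 0.01, taken as two-sided. **Assumed, because the SAP does not state them:** number of cases, test, direction of risk and coarseness of the values.

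**Formulas.** J(c) = sensitivity(c) + specificity(c) − 1, maximised over c (|J| if the data choose the direction). With A cases among n₁ patients on the high-risk side and C among n₂ on the other, RR = (A/n₁)/(C/n₂), and the Wald SE of log RR is √(1/A − 1/n₁ + 1/C − 1/n₂).

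**Check by hand, continuous values, no true effect.** The maximum of |J| is the two-sample Kolmogorov–Smirnov statistic. Let k = (cases × controls)/N. The chi-square z at a split leaving a fraction p on one side is J√k/√(p(1−p)), which is at least 2J√k. So z exceeds 2.576 whenever J√k > 1.288.

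- Direction fixed: P ≈ exp(−2 × 1.288²) = 0.036.
- Direction chosen by the data: P ≈ 2 × 0.036 = 0.072.

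These are large-sample lower bounds and do not depend on the case count.

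For the RR, take 100 cases and 501 controls: k = 100 × 501/601 = 83.4 and √k = 9.13. The Kolmogorov median is 0.828, so the median |J| is 0.828/9.13 = 0.091. At a central split, sensitivity is 0.545 and false-positive rate 0.455. Then RR = [54.5/(54.5 + 228.0)]/[45.5/(45.5 + 273.0)] = 0.193/0.143 = 1.35.

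**Calibration.** With a pre-set cut-off (N = 601, 10–30% cases, chi-square), the rejection rate is 0.008–0.012, so the nominal 0.01 is attained.

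**Simulation of the planned procedure, no true effect.** N = 500 or 601; 50, 100 or 180 cases; 2000 datasets per setting; Wald test of log RR at 0.01:

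| Values | Direction chosen by data | Direction fixed |
|---|---|---|
| Continuous | 0.11–0.13 | 0.07–0.08 |
| Rounded to SD/10 | 0.08–0.10 | 0.05–0.07 |
| Rounded to SD/3 | 0.05–0.07 | 0.04–0.05 |

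The median apparent RR is 1.22–1.76 overall and 1.33–1.45 at 100 cases; the true RR is 1. Repeat runs agree to within about 0.01 on the level and 0.02 on the RR.

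**With a real effect** (N = 601, 20% cases, direction chosen by data): a 0.2 SD shift gives a median apparent RR of 1.61 against 1.30 true at the chosen cut; a 0.4 SD shift gives 2.00 against 1.67.

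**Chance of at least one false positive over 24 null combinations** (N = 601, 100 cases, 500 datasets). For 24 independent tests truly at 0.01 it is 1 − 0.99²⁴ = 0.21. For the planned procedure:

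| Correlation within / between vital signs | Continuous, free | Continuous, fixed | SD/3, free | SD/3, fixed |
|---|---|---|---|---|
| 0 / 0 | 0.96 | 0.85 | 0.75 | 0.65 |
| 0.7 / 0 | 0.90 | 0.73 | 0.68 | 0.58 |
| 0.9 / 0 | 0.84 | 0.66 | 0.61 | 0.47 |
| 0.9 / 0.3 | 0.77 | 0.61 | 0.53 | 0.45 |

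A pre-set median split in the same data gives 0.17, 0.19, 0.12 and 0.08 down the rows.

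**NEWS-type reading** (n = 491, 80 assumed cases, equal information, pre-set cut at the 90th percentile). With no effect, the median RR is 1.54 by Youden against 0.99 at the pre-set cut. With a 0.3 SD shift it is 1.94 against 1.57.

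**The case against.** The case against does not dispute the mechanism; it disputes what can be built on it.

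- **The error rate is conditional.** The SAP names no test for the RRs and does not say that p<0.01 applies to them. That stands, so the error rate is stated only as what such a test would do. The RR bias needs no p-value.
- **The band is not a bound.** A wider grid (N = 400 or 601, 5–40% cases, chi-square, Wald or Fisher) ran from about 0.02, for coarse SpO₂-like values with fixed direction, to 0.17, for continuous values with 40% cases. No setting came down to 0.01.
- **601 is a ceiling.** Patients whose only SAE came later than 24 hours after monitoring are neither cases nor controls, and the 66% data rule removes more. Fewer patients or cases lowers the level somewhat in the coarsest settings but raises the apparent RR: with 30–180 cases among 400–601 patients, the median reached 2.09.
- **A second bias is not modelled.** Under Outcomes, cases contribute only the 24 hours before the event, less the last hour, while controls contribute every recorded 24-hour period. If the lowest value were taken across periods (assumed: two nights, correlation 0.7, 100 cases of 500), even a pre-set median split would give a median RR of 1.50 with no effect. This stands as a limit: the figures here isolate the cut-off search, and correcting for the search would not remove this other bias.
- **Direction of the bias.** With a fixed direction the bias is upward in that direction; only when the data choose the direction is it strictly away from 1.
- **NEWS.** No formal comparison is planned, so that part applies only if the figures are read side by side.

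**Conclusion.** The concern holds. Followed as written, the plan yields inflated RRs. Under the stated assumptions an uninformative vital sign gives a median RR of 1.22–1.76, and a p<0.01 test that ignores the search runs at about 0.04–0.13 per comparison. Coarser values, few cases or a conservative test can bring this to about 0.02–0.03, still at least twice nominal. If all 24 combinations were tested this way, the chance of at least one false positive is 0.45–0.96; the top figure assumes no correlation, and 0.45–0.77 applies at the most correlated setting tried.

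Confidence is high for the mechanism and for the fact of inflation. The exact figures depend on case count, coarseness of the values, direction and test, none of which the SAP gives. The RRs are secondary and the descriptive primary analysis is untouched, so this should be fixed but does not undermine the study as a whole.

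**What to change.** Keep the Youden cut-offs as descriptive output, and amend Secondary analyses as follows.

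1. **RR.** Re-select cut-off and direction inside every fold of a repeated 10-fold cross-validation, compute the RR from the held-out classifications, and bootstrap the whole procedure for the interval. With no effect (N = 601, 100 cases) this gave a median RR of 0.98–1.03. Bootstrap optimism correction is a weaker alternative, leaving 1.07–1.10. State that the cross-validated RR describes the selection procedure, not one published threshold.
2. **p-values.** Use a permutation test that repeats the cut-off search (level 0.008 at nominal 0.01), or keep the exposure continuous and report an RR per SD.
3. **Specification.** Name the test and the expected direction of risk for each vital sign.
4. **NEWS.** Set only corrected RRs beside the NEWS RR, within the n=491 cohort.

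At a minimum, label the uncorrected RRs as apparent and exploratory and report no p-values for them.

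**Cost.** SAP wording and some programming on existing data; nested resampling over 24 combinations takes computing time but no new data. The RRs will look less favourable and be less precise: with 50 cases of 500 and no effect, the cross-validated RR had a 5–95% spread of 0.49–1.94. The minimum option costs one sentence.

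### Window risk ratios are read at Youden cut-offs tuned on the same patients and the NEWS risk ratio at a preset alarm rule, so the two cannot be compared side by side

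*SAP*

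**What the plan says.** Under Secondary analyses, the SAP plans RRs and says that "Youden's optimal cut-off values will be calculated for each window-vital sign combination". It continues: "values for each patient are split into above or below Youden's optimal cut-off point, and risk ratios will be calculated from this discrimination". It states no hold-out sample, resampling or optimism correction, and plans no AUC, sensitivity or specificity to accompany the RR.

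The same section gives NEWS a different rule: "For NEWS measurements, a cut-off was defined as a total NEWS score" of at least 6, or one parameter scoring 3.

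The role of NEWS is stated once, under Exposures: "We also include manually measured NEWS values in the secondary analyses". No contrast, ranking or hypothesis of NEWS against the window values is written down. Under Patients, NEWS is available only for NCT03491137, which is 491 of 491 + 70 + 40 = 601 patients (82%).

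**The concern.** One RR analysis uses two cut-off rules. The Youden point is chosen by looking at who became a case, so the RR computed from it in the same patients is too high on average. The NEWS rule is set in advance and has no such inflation. The two rules also work at different operating points: a Youden cut-off on a moderately informative marker flags somewhat under half of patients, while an alarm rule may flag few. The RR alone shows neither difference.

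The SAP gives no other purpose for NEWS, which is not a circadian measure, so readers are likely to set its RR beside the window RRs and ask whether continuous circadian values do better than routine scoring. A larger window RR could then come from cut-off tuning alone. Similar RRs could hide that one rule finds most cases and the other few.

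**Working it through.** **Inputs.** From the SAP: the two cut-off rules, and 491 patients with NEWS. Not in the SAP, so assumed: case share p of 10, 15 or 20%; a shift of 0.3 or 0.5 SD between cases and controls, the same for NEWS and for one pre-named window value; correlation 0.3 between them; NEWS rule met by 5, 10 or 20% of patients. Both markers are treated as normal. The SAP states no case number, power or expected RR, so there is no planned figure to reproduce.

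**Step 1: true RR, without sampling error.** With sensitivity Se and specificity Sp, the share flagged is F = p·Se + (1 − p)(1 − Sp), and

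RR = [p·Se/F] ÷ [p(1 − Se)/(1 − F)] = Se(1 − F) / [(1 − Se)F].

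For a shift d the true Youden point lies at d/2, so Se = Sp = Φ(d/2). For d = 0.5 this is 0.5987, and for d = 0.3 it is 0.5596.

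Example cell (p = 15%, d = 0.5, NEWS flags 10%):

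- Youden: F = 0.15 × 0.5987 + 0.85 × 0.4013 = 0.4309. RR = 0.5987 × 0.5691 / (0.4013 × 0.4309) = 1.97.
- Fixed rule: a threshold of 1.378 SD gives Se = 0.190 and a false-positive share of 0.0841, so F = 0.15 × 0.190 + 0.85 × 0.0841 = 0.10. RR = 0.190 × 0.90 / (0.810 × 0.10) = 2.11.

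The same formula in other cells:

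| Cases | Shift | NEWS flags | Youden F | RR at Youden | Fixed-rule Se | RR at fixed rule |
|---|---|---|---|---|---|---|
| 10% | 0.3 | 5% | 0.452 | 1.54 | 0.084 | 1.73 |
| 10% | 0.5 | 5% | 0.421 | 2.05 | 0.112 | 2.40 |
| 15% | 0.5 | 10% | 0.431 | 1.97 | 0.190 | 2.11 |
| 20% | 0.5 | 20% | 0.441 | 1.89 | 0.324 | 1.91 |

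In all 18 cells (3 case shares × 2 shifts × 3 flag rates) the fixed rule has the larger true RR.

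**Step 2: RR as it would be reported.** Simulating the SAP's procedure with N = 491:

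- With a 0.3-0.5 SD shift, the window's RR exceeds the NEWS RR in about 61-84% of studies. A fair comparison would give 50%.
- With no association in either marker, it does so in about 77-92%.
- In the example cell the median RR is about 2.5 for the window (2.48 to 2.52 in separate runs) and 2.10 for NEWS. Against the true values, the window is inflated by a factor of about 2.5/1.97 = 1.27, and NEWS by 2.10/2.11, or not at all.
- Sensitivity in that cell is about 0.63 for the window and 0.19 for NEWS.

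**Step 3: where the lead comes from.** In the example cell, replacing the apparent window RR by the true RR at the cut-off actually chosen (median 1.98) lowers the share of studies in which the window beats NEWS from 74% to 42%. The lead is in-sample optimism.

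**Step 4: the optimism on its own.** With n = 601, 10, 20 or 30% cases and a marker unrelated to outcome, a Youden split gives a median RR of 1.59, 1.36 or 1.26, and p < 0.01 in 7.0-7.7% of runs. A preset cut-off gives a median of 0.98-1.00, and p < 0.01 in 0.6-1.2%.

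**Step 5: candidate remedies in the example cell.** Giving NEWS its own uncorrected Youden cut-off raises its median RR to about 2.5 against a true 1.97, so it only adds a second inflated figure. Setting the window cut-off to flag the same share as NEWS gives medians of 2.10 (window) and 2.13 (NEWS); across the cells the window wins 46-53% of the time.

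**The case against.** A reader might infer that the two rules favour the vital signs by construction. The documents do not support that. Youden maximises sensitivity plus specificity, not RR, and a strict preset rule can have the larger true RR, as Step 1 shows. Nor does the operating-point difference always push one way. At AUC 0.80 with 20% cases, the true RR is 4.56 at Youden against 4.10 for a cut-off flagging 5% of controls, but 5.54 for one flagging 50%. In a wider simulation with equal AUCs of 0.60 to 0.80 and n = 601, the Youden RR was the larger in most runs in 46 of 48 settings, and the fixed cut-off won in the other two.

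A reader might also infer that NEWS is the SAP's benchmark. The SAP never says so and plans no test between the two. The side-by-side reading is an inference from their sharing one RR analysis.

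The strongest defence is that a preset NEWS threshold is good practice: it is fixed in advance and carries no tuning. That stands, and the NEWS rule is not the fault. It is also fair that the real problem is the uncorrected Youden cut-off. Correcting it removes most of the apparent lead, but the two RRs would still describe rules that flag very different shares of patients, so correction alone does not make them comparable.

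Finally, the sizes rest on assumptions, and the model treats NEWS as one continuous score, whereas the SAP's rule is an ordinal total or a single-parameter score of 3.

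**Conclusion.** The point holds in limited form. The window RRs carry cut-off optimism that the NEWS RR lacks, and the two sit at different operating points, so the planned figures should not be compared directly. For two equally discriminating markers the window RR will usually look larger, in about 61-84% of studies under the stated assumptions, while its true value is somewhat smaller across that grid. The advantage is usual, not guaranteed, and in that grid it is due to in-sample tuning. Its size here depends on the case count, the discrimination of each marker and the share meeting the NEWS rule, none of which the SAP gives. As a secondary analysis with no planned contrast, this is a minor to moderate matter: worth correcting, but not a threat to the descriptive primary analysis.

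**What to change.** Keep the preset NEWS rule. In the NCT03491137 patients who have both measurements, add to Secondary analyses:

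1. the AUC of the total NEWS score and of each window-vital sign value;
2. each window-vital sign value's RR, sensitivity and specificity at the cut-off that flags the same share of patients as the NEWS rule, beside the same three figures for NEWS.

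State that any comparison of NEWS with the window values rests only on these. If no comparison is intended, say so, and say that the RRs are not to be read against each other. Correct every Youden-cut RR that is reported, for a vital sign or for NEWS, for optimism by bootstrap or cross-validation with the cut-off re-chosen in each resample. Do not add an uncorrected Youden RR for NEWS.

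The cost is a paragraph of SAP text, a resampling step and a few table columns, all from data already held. The vital-sign figures may look less favourable against NEWS as a result.
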